3.2 Informed Consent Process

All participants must be provided a consent form describing the study with sufficient information for participants to make an informed decision regarding their participation. Participants must sign the IRB approved informed consent prior to participation in any study specific procedure. The participant must receive a copy of the signed and dated consent document. The original signed copy of the consent document must be retained in the medical record or research file.

3.3 Study Timeline

Primary Completion:

We estimate the study will reach primary completion 27 months from the time the study opens to accrual.

Study Completion:

The study will reach study completion 36 months from the time the study opens to accrual.

4.0 TREATMENT PLAN

All patients will have a diagnosis of ameloblastoma pathologically confirmed by the participating institution's department of pathology. The mutational status of BRAF in the tumor must be determined by any CLIA-certified lab using standard techniques. These may include, for example, Sanger sequencing, SNaPshot platform, immunohistochemistry, Foundation One tests, etc.). While we are primarily expecting to identify V600 E mutations, other BRAF mutations known to confer sensitivity to dabrafenib are acceptable if approved by the study principal investigator.

Every patient must have baseline blood chemistries and counts and other eligibility criteria as defined in Section 3 done according to the schedule defined in the study calendar in Section 9. Baseline imaging used to define RECIST v1.1 {Eisenhauer, 2009} measurements are at the discretion of the local investigator. These will typically be either a contrast enhanced CT or MRI of the relevant anatomy, but PET-CT is also appropriate if the lesion is evaluable by PET-CT per RECIST v1.1 criteria. To maintain consistency of data and quality of science, whatever imaging modality is used at baseline for each patient should be used throughout the trial. Photographic documentation is encouraged but cannot substitute for imaging.

The starting dose for all patients will be:

Dabrafenib, 150 mg orally twice daily taken at least 1 hour before or at least 2 hours after a meal. Dabrafenib comes as 75 mg and 50 mg capsules. Therefore the initial dose will be two 75 mg capsules as specified above. The second dose of dabrafenib (150 mg) should be administered approximately 12 hours after the morning dose.

Trametinib 2 mg once daily.

Take the once-daily dose of trametinib at approximately the same time each day with either the morning dose or the evening dose of dabrafenib. Study medications should be taken orally with approximately 200 mL of water under fasting conditions, **either 1 hour before or 2 hours after a meal.**

If a subject vomits after taking study medication, the subject should be instructed **not** to retake the dose and should take the next dose as originally scheduled.

If administration of trametinib is interrupted or permanently discontinued, administration of dabrafenib may be continued. If administration of dabrafenib is interrupted or permanently discontinued, administration of trametinib may continue.

If a subject misses a dose of dabrafenib, the subject may take the dose immediately if the next dose is scheduled for at least 6 hours later. If the next scheduled dose of dabrafenib is due in less than 6 hours, the subject should skip the dose and resume dabrafenib dosing at the next scheduled dose. If a subject misses a dose of trametinib, the subject may take the dose immediately if the next dose is scheduled for at least 12 hours later.

Patients whose tumors are amenable to surgical resection will continue dosing continuously for at least 6 weeks and proceed to surgery between weeks 6 and 7, without dose interruption. Patients undergoing surgical resection will continue dabrafenib and trametinib until it is necessary to take nothing by mouth in the hours preceding surgery, but **ideally the patients will be dosed with dabrafenib and trametinib within 12 hours of the surgical resection**. Patients whose tumors are grossly completely resected will not resume dabrafenib and trametinib. Patients whose tumors are not resected completely have the option to resume the dabrafenib and trametinib at the dose they were receiving immediately prior to surgery if ALL of the following criteria are met:

1. Prior to surgery the patient did not have AEs or progression which necessitated dabrafenib or trametinib cessation.
2. The patient has recovered from surgery without unexpected complication.
3. At least 1 week has passed since surgery.
4. The patient has evaluable residual tumor.
5. No more than 6 weeks has elapsed since surgery.

Patients whose disease is judged to be not amenable to resection will continue dabrafenib and trametinib indefinitely as long as there has not been tumor progression either by RECIST v1.1 or clinical progression criteria, there have not been unacceptable adverse events and the patient has not decided to discontinue for other reasons.

Clinical evaluations for protocol purposes will take place according to the schedule defined in Section 9. Dose modifications will be according to the guidelines in Section 6.

4.1 General Concomitant Medication and Supportive Care Guidelines

4.1.1 Permitted Medications and Non-Drug Therapies

The investigator must be informed as soon as possible about any medication taken from the time of screening until the end of investigational drug administration. Documentation of concomitant medication(s), including dietary supplements, taken during the study will be recorded in the patient medical record according to the schedule specified in Section 9. The minimum requirement is that drug name, dose, and the dates of administration are to be recorded.

Subjects should receive full supportive care during the study, including transfusions of blood and blood products, and treatment with antibiotics, anti-emetics, anti-diarrheals, and analgesics, and other care as deemed appropriate, and in accordance with their institutional

guidelines. Use of anticoagulants such as **warfarin is permitted however, caution should be exercised** and additional International Normalized Ratio (INR) monitoring is recommended when dabrafenib is used concomitantly with warfarin. See Section 4.1.3 for guidelines concerning concomitant warfarin and dabrafenib administration.

Radiation skin injury has been reported with concurrent use of dabrafenib and radiation. It is recommended that dabrafenib and trametinib be held for 7 days before and 2 days after XRT.

Medicinal products that increase gastric pH should be used with caution when administered with dabrafenib. See Section 4.1.3 for details.

4.1.2 Prohibited Medications and Non-Drug Therapies

The use of certain medications (see Table 2 below) and illicit drugs within 28 days or 5 half-lives, whichever is shorter, prior to and during dabrafenib study treatment, will not be allowed.

The following medications or non-drug therapies are prohibited while on treatment in this study:

- Other anti-cancer therapies;
- Other investigational drugs;
- Herbal remedies (eg, St John's wort);
- Dabrafenib is metabolized primarily by Cytochrome P450 (CYP) 2C8 and CYP3A4. Co-administration of dabrafenib with ketoconazole, a CYP3A4 inhibitor, or with gemfibrozil, a CYP2C8 inhibitor, resulted in increases in dabrafenib AUC of 71% and 47%, respectively. Drugs that are strong inhibitors or inducers of CYP3A and CYP2C8 (see list in the table below) may only be used under special circumstances (e.g. as a single use for a procedure) while treatment with study drug is interrupted as they may alter dabrafenib concentrations; consider therapeutic substitutions for these medications. **Approval of the protocol principal investigator is required and must be documented in these situations.**

Table 2 : Prohibited Medications

PROHIBITED – Strong inducers of CYP3A or CYP2C8, since concentrations of dabrafenib may be decreased	
Class/Therapeutic Area	Drugs/Agents
Antibiotics	Rifamycin class agents (eg, rifampin, rifabutin, rifapentine),
Anticonvulsant	Carbamazepine, oxcarbazepine phenobarbital, phenytoin, s-mephenytoin
Miscellaneous	bosentan, St-John’s wort
PROHIBITED – Strong inhibitors of CYP3A, or CYP2C8 since concentrations of dabrafenib may be increased	
Class/Therapeutic Area	Drugs/Agents
Antibiotics	Clarithromycin, telithromycin, troleandomycin
Antidepressant	Nefazodone
Antifungals	Itraconazole, ketoconazole, posaconazole, voriconazole
Hyperlipidemia	Gemfibrozil
Antiretroviral	ritonavir, saquinavir, atazanavir
Miscellaneous	Conivaptan

4.1.3 Medications to be used with Caution

The following medications should be used with caution as their concentrations may be altered by dabrafenib or they may alter dabrafenib concentrations:

- Drugs that are moderate inhibitors or inducers of CYP3A and CYP2C8 as they may alter concentrations of dabrafenib.
- Dabrafenib has been shown to induce CYP3A4 and CYP2C9 in vivo using midazolam (CYP3A4 substrate) and S-warfarin (CYP2C9 substrate). Dabrafenib is an in vitro inducer of CYP2B6 and other enzymes such as CYP2C8, CYP2C19, UDP-glucuronyl transferases. Transporters may also be affected. Co-administration of dabrafenib and medications which are affected by the induction of these enzymes (including warfarin) and transporters may result in loss of efficacy. If co-administration of these medications is necessary, investigators should monitor subjects for loss of efficacy or consider substitutions of these medications. A partial list of these medications is provided in Table 2 above.
- Therapeutic level dosing of warfarin can be used with close monitoring of PT/INR by the site. Warfarin exposure has been shown to decrease (37% decrease) due to dabrafenib-mediated enzyme induction. Conversely, if dabrafenib dosing is reduced, interrupted, or discontinued, warfarin exposure may be increased. Thus, warfarin dosing may need to be adjusted based on PT/INR during and after treatment with dabrafenib. Prophylactic low dose warfarin may be given to maintain central catheter patency.

- InfromDabrafenib solubility is pH-dependent with decreased solubility at higher pH. Drugs such as proton pump inhibitors that inhibit gastric acid secretion to elevate gastric pH may decrease the solubility of dabrafenib and reduce its bioavailability. No clinical study has been conducted to evaluate the effect of pH on dabrafenib pharmacokinetics. In an ad-hoc analysis, no differences in C_{max} and AUC were noted between subjects who reported taking pH-elevating products relative to other subjects. Due to the theoretical risk that pH-elevating agents may decrease oral bioavailability and exposure to dabrafenib, these **medicinal products that increase gastric pH should be used with caution when administered with dabrafenib.**

4.2 Criteria for Removal from Study

Patients should have dabrafenib discontinued for unacceptable adverse events, clinically unacceptable or RECIST v1.1 defined progression, or patient withdraws of consent. For patients who stop dabrafenib because of unacceptable AEs or progression of disease, providers may proceed to surgical resection as clinically indicated. Patients who have not withdrawn consent to be studied should have all planned restaging and secondary tissues analyses performed per protocol prior to surgery and on the surgical specimens resected at the time of surgery. Patients should be followed for protocol related AEs for 4 weeks after the last dabrafenib dose unless another systemic anti- cancer agent has been initiated.

5.0 STUDY AGENT INFORMATION

5.1 Study Agents

Dabrafenib is a kinase inhibitor FDA approved for the treatment of patients with unresectable or metastatic melanoma with BRAF-V600E mutation as detected by an FDA-approved test. It comes in 50 mg and 75 mg capsules. Active ingredient: dabrafenib. Inactive ingredients: colloidal silicon dioxide, magnesium stearate, microcrystalline cellulose. Capsule shells contain: hypromellose, red iron oxide (E172), titanium dioxide (E171).

Trametinib is a FDA-approved kinase inhibitor for the treatment of patients with unresectable or metastatic melanoma with BRAF-V600E or -V600K mutations as detected by an FDA-approved test. Tablets are supplied as 0.5 mg and 2 mg tablets for oral administration. Each 0.5 mg tablet contains 0.5635 mg trametinib dimethyl sulfoxide equivalent to 0.5 mg of trametinib non-solvated parent. Each 2 mg tablet contains 2.254 mg trametinib dimethyl sulfoxide equivalent to 2 mg of trametinib non-solvated parent. The inactive ingredients are tablet core: mannitol, microcrystalline cellulose, hypromellose, croscarmellose sodium, magnesium stearate (vegetable source), sodium lauryl sulfate, colloidal silicon dioxide; and coating: hypromellose, titanium dioxide, polyethylene glycol, polysorbate 80 (2 mg tablets), iron oxide yellow (0.5 mg tablets), iron oxide red (2 mg tablets).

Dabrafenib and trametinib will be dosed as specified in Section 4 of this protocol, with dose modifications in Section 6.

5.2 Availability

Dabrafenib and trametinib will be obtained from Novartis and distributed to all investigational sites according to a pharmacy appendix to be developed prior to protocol activation.

5.3 Agent Ordering

Dabrafenib and trametinib will be ordered by site investigational pharmacies according to guidelines to be developed prior to protocol activation and included in the pharmacy appendix section.

5.4 Agent Accountability

Access to dabrafenib and trametinib will be restricted according to the standard operating procedures of the investigational pharmacies of each collaborating institution's pharmacy. Drug accountability will similarly be according to each institution's standard operating procedures.

5.5 Combination Dosage and Administration and Handling and Storage Guidelines

Dabrafenib and trametinib must be dispensed and administered in accordance with the protocol, and only to subjects enrolled in the study. Dabrafenib and trametinib must be stored in a secure area under the appropriate physical conditions for the product. Study medication is to be stored at the temperature specified on the label. Maintenance of a temperature log (manual or automated) is required. Access to and administration of dabrafenib and trametinib will be limited to the investigator and authorized site staff.

6.0 DOSE MODIFICATIONS

6.1 Dose Modification for General Toxicities

General guidelines regarding management and dose reduction for adverse events that are considered by the investigator to be related to study treatment and for which specific guidelines do not apply are provided in the table below. These guidelines are intended primarily for toxicities not easily managed with routine supportive care. For example, alopecia is not an indication for dose modification, nor is grade 2 nausea and vomiting that can be easily managed with anti-emetics.

Table 3: Recommended dabrafenib and trametinib dose level reductions

DABRAFENIB		TRAMETINIB	
Dose Level	Dose/Schedule	Dose Level	Dose/Schedule
Full dose	150 mg twice daily	Full dose	2 mg once daily
First reduction	100 mg twice daily	First reduction	1.5 mg once daily
Second reduction	75 mg twice daily	Second reduction	1 mg once daily
Third reduction	50 mg twice daily	Third reduction	0.5 mg once daily

Table 4: Dose Modification Guidelines - General

CTCAE Grade	Occurance	Action and Dose Modification ^{a,b}
Grade 1 or Grade 2 (tolerable)	N/A	Continue study treatment at same dose level (no dose modification) and monitor as clinically indicated
Grade 2 (Intolerable) or Grade 3	1 st , 2 nd or 3 rd occurrence	Interrupt study treatment until toxicity resolves to ≤ grade 1 then restart at next lower dose level
	4 th or greater occurrence	Discontinue treatment
Grade 4	1 st occurrence	Interrupt study treatment until toxicity resolves to ≤ grade 1 or baseline then restart at next lower dose level or discontinue at discretion of investigator
	2 nd occurrence	Interrupt study treatment until toxicity resolves to ≤ grade 1 or baseline then restart at two dose levels lower than the starting dose or discontinue at discretion of investigator and after discussion with the medical monitor.
	3 rd occurrence	Discontinue treatment

- a. Treatment should be discontinued if more than 3 dose reductions are required
- b. Approval from the protocol PI is required to restart study treatment after ≥ 21 days

When an individual’s adverse reactions are under effective management, dose re-escalation following the same dosing steps as de-escalation may be considered.

These are general guidelines and investigators should always use clinical judgment in determining dose adjustments for any individual patient. Some toxicities may require hospitalization for stabilization, additional work-up, and consultation with a specialist before treatment can be restarted. Specific adverse events and recommended management include the following:

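### Minor: Table 4's only restart dose after a second Grade 4 event is 75 mg BID / 1 mg, which is no cut for a patient or drug already at that level

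*Combined protocol and SAP*

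**What the plan says.** Section 6.1, Table 3 of the combined protocol and SAP gives three reductions from full dose (dabrafenib / trametinib): 100 mg BID / 1.5 mg, 75 mg BID / 1 mg and 50 mg BID / 0.5 mg.

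Table 4 says how to move down this ladder. It covers treatment-related toxicities "for which specific guidelines do not apply are provided in the table below", so events with their own table in Section 6.2 fall outside it. For Grade 3 or intolerable Grade 2 events, first to third occurrence, treatment is held until the toxicity falls to at most "grade 1 then restart at next lower dose level". The first Grade 4 event also steps down one level, with discontinuation as an option. For the second Grade 4 event, the reference point changes: hold, "then restart at two dose levels lower than the starting dose", or discontinue after discussion with the medical monitor. A third Grade 4 event ends treatment. Footnote a adds: "Treatment should be discontinued if more than 3 dose reductions are required".

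Section 4.0 fixes the reference dose. Under "The starting dose for all patients will be" it lists dabrafenib 150 mg twice daily and trametinib 2 mg once daily, with no other starting level.

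**The concern.** Two rows of one table count from different places. The Grade 3 row and the first Grade 4 row count from the current dose; the second Grade 4 row counts from the starting dose. The two agree while the patient is one level down. They part once the patient, or either drug, is at the second reduction. There the row written for the more severe event names a restart dose equal to the one at which that event occurred, while the row for the less severe event still lowers the dose.

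What is at stake is the safety of an individual patient restarted after a second Grade 4 event. No efficacy result depends on it.

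**Working it through.** The plan states no figure on this point, so there is none to reproduce. The check walks the Table 3 ladder through the Table 4 rows. Call full dose level 0 and the reductions levels 1, 2 and 3.

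**Rules**
- Grade 3 row: new level = current level + 1.
- First Grade 4: new level = current level + 1.
- Second Grade 4: new level = 0 + 2 = 2, whatever the current level.

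**Is level 2 reachable before a second Grade 4 event?** Yes. Grade 3 then Grade 4, or the reverse, gives 150/2 → 100/1.5 → 75/1. Only two reductions have been used, so footnote a does not apply. With two Grade 4 events and nothing else, the path is 150/2 → 100/1.5 → 75/1, a true cut, and there is no problem.

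**Cut at the second Grade 4 event, against the Grade 3 row at the same level (dabrafenib / trametinib)**

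| Current level | Second Grade 4 row | Grade 3 row |
|---|---|---|
| 0 (after re-escalation), 150/2 | to 75/1: −50% / −50% | to 100/1.5: −33% / −25% |
| 1, 100/1.5 | to 75/1: −25% / −33% | to 75/1: −25% / −33% |
| 2, 75/1 | to 75/1: 0% / 0% | to 50/0.5: −33% / −50% |

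The row is stricter than the Grade 3 row at level 0, equal at level 1 and weaker at level 2.

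**One drug alone.** Suppose trametinib is cut once for Grade 2 pneumonitis (Table 10) and not re-escalated, and both drugs are then cut for a first Grade 4 event. The patient is at 100 mg BID / 1 mg. A second Grade 4 event gives 75 mg BID / 1 mg: dabrafenib falls 25%, trametinib 0%. A dabrafenib-only cut for pyrexia (Table 7) produces the mirror image.

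**How many patients?** The documents give no rate for the affected state. They do list Grade 4 events in the pooled combination patients: Table 19, 4 + 4 + 3 + 3 + 2 + 1 = 17; hypophosphatemia in Table 15, 1; headache in Table 14, 1; hemorrhage in Table 18, 2. The total is 21.
- 21 / 559 = 3.8%, assuming each event is in a different patient.
- 3.76% × 21 enrolled = 0.79 patients with a *first* listed Grade 4 event; × 17 evaluable = 0.64.
- Without the 4 hyperglycemia events, which Section 6.2.4 covers: 17 / 559 × 21 = 0.64.
- Some laboratory denominators are 556 rather than 559; 0.79 is unchanged to two decimals.

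These figures count first Grade 4 events only. The affected state also needs a separate reduction and a second Grade 4 event, so it is expected in well under one patient. The lists cover selected reactions in melanoma patients without adjustment for exposure, and I would not put a narrower number on it.

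**The case against.** The best argument against the point is about counting. Table 4 does not say whether occurrences are counted within a grade or across grades. If across, a Grade 3 event followed by a Grade 4 event makes the latter a second occurrence (75/1), and the next Grade 4 event is a third, which ends treatment; the two-drug path disappears. But the table is laid out by grade with occurrences numbered inside each grade, so counting within grade is the natural reading. Counting across grades also leaves the one-drug cases, because cuts under Tables 7 and 10 are made outside Table 4.

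It is also fair to compare the rows whole. The second Grade 4 row carries a discontinuation option and a medical monitor discussion that the Grade 3 row lacks for its first three occurrences, and Grade 4 stops one occurrence sooner. Section 6.1 calls these general guidelines subject to clinical judgment, footnote b requires approval from the protocol PI to restart after 21 days or more, and Section 4.2 states: "Patients should have dabrafenib discontinued for unacceptable adverse events". All of this stands and is why the point is minor. None of it names a lower restart dose.

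Three stronger readings might be inferred, and the documents do not support them:
- *The protocol forces a same-dose restart.* It does not; discontinuation is in the same cell.
- *A same-dose restart is itself an error.* Table 5 at Grade 4, Table 7 after the first two uncomplicated fevers, Table 8 footnote b and Table 9 all allow one. There it is written as the action or an option; in Table 4 it follows only from where the row starts counting.
- *At the third reduction the row raises the dose, from 50/0.5 to 75/1.* Taken in isolation it would, but a further cut there would be a fourth reduction, and footnote a then calls for discontinuation.

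**Conclusion.** The row is wrong as written, and the matter is minor. For a patient or drug already at the second reduction, the only restart dose named after a second Grade 4 event is the current one, against 50 mg BID / 0.5 mg after a Grade 3 event. This rests on the starting dose being fixed for everyone, on occurrences being counted within grade for the two-drug case (the one-drug case does not need that), and on the investigator choosing to restart.

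The people exposed are few. Resectable patients "proceed to surgery between weeks 6 and 7, without dose interruption", which leaves little time for three such events with holds between them, so the case mainly concerns unresectable patients treated indefinitely and those who resume after incomplete resection. The 0.79 figure should not be read as the number affected; it counts first Grade 4 events. The primary endpoint, the sample size and the stated error rates (0.0466 type I error, 0.8122 power) do not depend on this row.

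**What to change.** In the Grade 4 second-occurrence cell of Table 4, change the restart instruction to: restart each drug at the lower of two dose levels below its starting dose and one dose level below its current dose. Keep the discontinuation option, the investigator's discretion and the medical monitor discussion.

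For each drug at level 0, 1 or 2, the new level is the larger of 2 and current level + 1. Levels 0 and 1 still restart at level 2, level 2 moves to level 3 (50 mg BID / 0.5 mg), and the split case 100/1 goes to 75/0.5 instead of 75/1.

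Leave footnote a to govern patients already at the third reduction. Section 4.0 says "If administration of dabrafenib is interrupted or permanently discontinued, administration of trametinib may continue", and allows the reverse, but footnote a speaks of treatment as a whole. Whether one drug may go on when the other has run out of levels is a separate decision that this edit need not make.

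The cost is a wording change in one table cell at the next amendment, with no added patients or procedures. The downside is a lower dose for the very few patients affected.
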